APPENDIX 1. ANALYSIS VISIT WINDOWS

Analysis visits are defined by the windows that will have the widths of the corresponding assessments centered at the scheduled time. Unscheduled visits within a visit window defined below will be grouped into the closest scheduled visits based on the visit date.

Table 1: Analysis Visit Window for Vital Signs

Analysis Visit	Target Day in OLE	Start Day	End Day
Baseline	See Sec	tion 5.3.2	
EX-Day 1 (postdose) [#]	1	1	1
EX-Week 3 (predose and postdose)	22	2	32
EX-Week 3*n (predose and postdose)	21*n+1	21*n-9	21*n+11
EX-28 Days post last dose [@]			**

^{**} end of OLE period

Table 2: Analysis Visit Window for PFT and Weight [#]

Analysis Visit	Target Day	Start Day	End Day
Baseline		See Section 5.3.2	
EX-Week 24	169	2	253
EX-Week 24*n [\$]	24*n+1	24*7*n-82	24*7*n+85

^[\$] n is 2, 3, 4, etc.

Note: The timing of PFT is dependent on local schedules.

Table 3: Analysis Visit Window for HRCT

Analysis Visit	Target Day	Start Day	End Day
Baseline		See Section 5.3.2	
EX-Week 24	169	2	253
EX-Week 24*n [\$]	24*n+1	24*7*n-82	24*7*n+85
EX-28 days Post last dose [@]			**

^{**} end of OLE period

Note: The timing of HRCT is dependent on local schedules.

^[\$] n is 2, 3, 4, etc.

^[@] Same as visit collected on CRF.

^[#] Weight baselines follow same rules as vital signs.

^[\$] n is 2, 3, 4, etc.

^[@] Same as visit collected on CRF.

APPENDIX 2. ANALYSIS OF ASSOCIATION BETWEEN QLF AND OS

Cox proportional hazard (PH) analyses on the association between QLF and overall survival (OS) will be performed for the ITT population including both double-blind and OLE periods. The hazard ratio and its corresponding 95% CI between QLF Test Group vs QLF Reference Group. A stratified log-rank test stratified by randomization stratification factor will be used for treatment comparison.

No imputation will be performed on missing data. On-treatment analysis will be optional.

- QLF as a predictor:
- 1. To investigate whether baseline QLF is a significant predictor of mortality, a Cox PH model will include electronic data capture (EDC) GAP stage (I/II/III), and prior IPF treatment (Yes/No) as covariates, baseline QLF% (cutoff such as 15%, 20%, or 25%) as the predictor variable.
- 2. Similar analysis on baseline QLF volume (ml) will be performed as in 1), using baseline QLF volume (ml) (cutoff such as 300ml, 400ml, and 500ml) as the predictor variable.
- 3. In addition, Cox PH model including EDC GAP stage (I/II/III), and prior IPF treatment (Yes/No) as covariates, baseline QLF% or QLF volume (ml) (as a continuous variable) as the predictor variable, will be performed.
 - Change from baseline in QLF at Week 24 as a predictor
- 1. In addition, to investigate the association between change from baseline in QLF% (baseline to Week 24) and OS, the Cox PH model will include EDC GAP stage (I/II/III), prior IPF treatment (Yes/No), and baseline QLF% (as a continuous variable) as covariates, and category in change from baseline in QLF% (e.g., ≥2% vs <2%) as the predictor variable.
- 2. Similar analysis on QLF volume (ml) change from baseline will be performed as in 4) with baseline QLF% replaced with baseline QLF volume as a continuous covariate, and change from baseline in QLF volume (ml) as the predictor variable with a cutoff (e.g., ≥40 mL vs <40mL) will be performed.

STATISTICAL ANALYSIS PLAN

TITLE PAGE

A Phase 3, Randomized, Double-Blind, Placebo-

STUDY TITLE: Controlled Efficacy and Safety Study of Pamrevlumab in

Subjects with Idiopathic Pulmonary Fibrosis (IPF)

PROTOCOL NUMBER: FGCL-3019-095 (ZEPHYRUS 2)

FibroGen, Inc.

STUDY SPONSOR: [name]

[name]

STUDY DRUG: Pamrevlumab

INDICATION: Idiopathic Pulmonary Fibrosis (IPF)

PROTOCOL VERSION: Version 2.0

SAP VERSION Final V1.0 (Double-Blind Period)

RELEASE DATE: 12Jun2023

CONFIDENTIALITY STATEMENT

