5.3.4. General Instructions of TLF

Follow the same guidelines as described in SAP for the double-blind period.

Summary tables will be presented for each previous actual treatment group in the double-blind period and all subjects pooled in the OLE period.

Efficacy and safety data will be summarized descriptively for subjects who entered OLE. No formal statistical inference will be performed.

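### OLE SAP Appendix 2 leaves its QLF cut-offs open, names no deciding model for whether QLF predicts mortality, and analyses Week 24 change in QLF only as a dichotomy

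*SAP*

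**What the plan says.** OLE SAP Appendix 2 plans Cox models relating QLF to overall survival in the ITT population, over the double-blind and OLE periods together. For baseline QLF:

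- **Item 1** states the aim: "To investigate whether baseline QLF is a significant predictor of mortality". It adjusts for GAP stage and prior IPF treatment and uses "baseline QLF% (cutoff such as 15%, 20%, or 25%) as the predictor variable".
- **Item 2** repeats this for volume, "using baseline QLF volume (ml) (cutoff such as 300ml, 400ml, and 500ml) as the predictor variable".
- **Item 3** adds the same model with "baseline QLF% or QLF volume (ml) (as a continuous variable) as the predictor variable, will be performed".

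For change from baseline to Week 24 there are two models. One uses "category in change from baseline in QLF% (e.g., ≥2% vs <2%) as the predictor variable"; the other uses "change from baseline in QLF volume (ml) as the predictor variable with a cutoff (e.g., ≥40 mL vs <40mL". Neither has a continuous counterpart.

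The appendix gives no alpha, no multiplicity rule and no event count, and it does not say which model answers the question in item 1. Section 5.3.4 of the same SAP says of data from subjects who entered the OLE: "No formal statistical inference will be performed".

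**The concern.** Item 1 poses a yes/no question about significance, and several models then answer it. The words *such as* and *e.g.* allow cut-offs other than those listed. Even item 3 says QLF% **or** volume, so the measure is open too. A nominal Cox p-value, or a 95% CI that excludes 1, holds its level only for one cut-off fixed in advance. If the conclusion could rest on whichever cut-off turned out significant, chance findings would be more frequent than the nominal level implies.

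The Week 24 models raise a second problem. Cutting change in QLF into two groups discards information, and no planned model recovers it. A real gradient with survival could be missed.

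What is at stake is how far a statement that QLF does or does not predict death can be trusted. QLF volume is a secondary endpoint of the trial, so readers may carry such a statement over to it.

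**Working it through.** **Inputs.** Appendix 2 contains no error rate, power or event count, so there is no figure of its own to reproduce. From the documents: three QLF% cut-offs, three volume cut-offs, one cut-off for each change measure, the GAP-stage and prior-treatment covariates, and N = 340 (protocol Section 8.1, sized for FVC). Assumed: two-sided 0.05 per test (the appendix reports 95% CIs), the share of subjects above each cut-off, the correlation of QLF% with QLF volume, and the death rate.

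**1. Three QLF% cut-offs, any one significant.** Under no association, Cox score statistics at nested cut-offs are approximately jointly normal. If p_hi and p_lo are the larger and smaller shares above two cut-offs, their correlation is √[p_lo(1−p_hi) / (p_hi(1−p_lo))]. For shares of 75/50/25%:

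- adjacent cut-offs: √[0.5×0.25 / (0.75×0.5)] = 0.58
- outer cut-offs: 0.25/0.75 = 0.33

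The probability that any |Z| exceeds 1.96, by Monte Carlo:

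| Shares above the three cut-offs | P(any significant) |
|---|---|
| 55/50/45% | 8.6% |
| 60/50/40% | 10.1% |
| 75/50/25% | 12.4% |
| 60/35/15% | 12.4% |
| 90/50/10% | 13.6% |

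Three independent tests would give 1 − 0.95³ = 14.3%. The Bonferroni ceiling is 3 × 5% = 15%.

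**2. Finite-sample check.** Cox models were simulated with N = 340, GAP stage and prior treatment as covariates, about 58 deaths in the last simulated set, and 1,000 replicates. Any of three cut-offs was significant in 10.7% (shares 60/50/40%) and 11.9% (75/50/25%). The middle cut-off alone gave 5.3% and 6.0%, and the continuous predictor 4.3% and 5.7% (Monte Carlo SE about 0.7 points for a 5% rate).

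**3. Six baseline cut-offs.** The double-blind SAP (Section 6.7.2.2.4.1) defines QLF volume as total lung capacity volume times QLF%, so the two measures are related. The documents give no correlation, so 0.70 to 0.95 was tried:

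| Shares (same for both measures) | Correlation 0.70 | Correlation 0.95 |
|---|---|---|
| 60/50/40% | 17.6% | 14.8% |
| 75/50/25% | 21.2% | 18.6% |
| 90/50/10% | 23.9% | 21.0% |

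**4. Cost of dichotomising.** For a normal predictor with a log-linear effect, splitting with share p above the cut-off c keeps a fraction E = φ(c)² / [p(1−p)] of the information. If the continuous test has 80% power, the split has power Φ[(1.960 + 0.842)√E − 1.960].

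- Median split: E = 0.637; Φ(2.802 × 0.798 − 1.960) = Φ(0.28), about 61%.
- 25/75 split: E = 0.539, about 54%.
- 10/90 split: E = 0.342, about 37%.

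The share of subjects that 2% or 40 mL would separate is not in the documents.

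**5. After the change.** One pre-specified continuous test has a 5% error rate, in line with the simulated 4.3% and 5.7%. Testing QLF% and volume both at 0.05 would give 1 − 0.95² = 9.75% if they were independent, which is why one measure should be named.

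**The case against.** The strongest reply is that the SAP never says any significant cut-off will do. It states no alpha and no selection rule, and it names a hazard ratio with 95% CI as the output. The only test it names, a stratified log-rank, is for treatment comparison. The *or* in item 1 could mean that a single cut-off will be chosen. This stands: the rates above are conditional and are not properties of the plan as written. It does not close the gap, because item 1 asks about significance, a 95% CI can be read as a test, and nothing says how or when a cut-off would be chosen.

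Second, item 3 already plans continuous baseline models. This stands in full. A reader might infer that the plan loses power for baseline QLF; it does not, because the continuous model will be run. The loss is unremedied only for Week 24 change.

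Third, the analysis lies outside the fixed sequence (double-blind SAP Section 6.7, Table 3) and is not a protocol endpoint. This also stands, so a reader who inferred a threat to the trial's type I error would be wrong. The disclaimer in Section 5.3.4 settles less: it follows a sentence about subjects who entered the OLE, whereas Appendix 2 uses the ITT population.

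Two further readings go too far. One is that the false-positive rate simply is two to four times 5%. Three QLF% cut-offs cannot exceed three times, four times needs both measures pooled, and either figure needs the unstated rule. The other is that the analysis is meant to establish QLF as standing in for survival; no document says so.

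**Conclusion.** The point holds as a minor one. Appendix 2 asks a significance question without naming the model that answers it, and it leaves the cut-offs open. If any nominally significant cut-off were accepted, the false-positive rate would be about 9-14% for the three QLF% cut-offs and about 15-24% for the six baseline cut-offs. That rests on two-sided 0.05 per test, assumed shares above the cut-offs, and an assumed correlation of 0.70-0.95 between the measures. Week 24 change is analysed only as a dichotomy. For a normal predictor with a log-linear effect, that takes 80% power to about 61% at a median split and to about 37% at a 10/90 split. No treatment claim depends on this analysis.

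**What to change.** In OLE SAP Appendix 2:

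1. Make the item 3 continuous Cox model, for one pre-specified measure, the single test of baseline QLF. QLF volume is the natural choice because it is the trial's secondary endpoint; QLF% is then supportive.
2. Add continuous change in QLF at Week 24 as the tested predictor, with the covariates already planned, and name the measure there too.
3. Delete *such as* and *e.g.* so that the listed cut-offs are fixed. Report those groupings descriptively (hazard ratio, 95% CI, Kaplan-Meier curves) with no claim of significance.
4. Reconcile item 1's aim with Section 5.3.4: say whether Appendix 2 is exempt from the disclaimer and, if so, at what alpha the deciding test is read.

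The cost is SAP wording and the added Week 24 models; the continuous baseline models are already planned. The small downside is that a continuous predictor assumes a log-linear effect, which one added quadratic or spline term can check.

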4.4. Subject Study Withdrawal Procedures/Assessments

Subjects who terminate / withdraw from the study early, for any reason, will have an Early Study Termination (ET) visit as soon as feasible. Study procedures to be performed during the ET visit can be found in the SOA (Appendix 1). At the ET visit, PFTs and questionnaires do not have to be repeated, if the last one (excluding screening visit) was performed within 8 weeks of this visit; HRCT does not have to be repeated, if the last one (excluding the screening visit) was performed within 4 months of this visit.

These subjects will have a safety follow-up visit 28 days after the last dose. A follow-up phone call 60 days after last dose will also be completed for a final assessment of safety.

In addition, these subjects should be contacted by phone for vital status at weeks 24 and 48. These subjects will not be eligible for the OLE phase.

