6.7.2.1.4. Analysis Variables

6.7.2.1.4.1. Time (Days) to disease progression

Time (Days) to disease progression is defined as the number of days from randomization to either the first occurrence of an absolute ≥10% decline from baseline in FVCpp or all-cause death based on observed data, whichever occurs earlier during the on-study period as described in Section 5.3.1.1. Subjects who die without any post-baseline PFT assessments will be considered as an event on the date of death.

Subjects without an event will be censored on the date of the last PFT assessment after randomization in the double-blind period. Alive/Censored subjects without any post-baseline PFT assessments will be censored on Day 1.

6.7.2.1.4.2. Time (Days) to the first occurrence of any component of the clinical composite endpoint: acute IPF exacerbation, respiratory hospitalization, or death

Time (Days) to the occurrence of any component of the clinical composite endpoint is defined as the number of days from randomization to either the first occurrence of acute IPF exacerbation (including both confirmed and suspected cases), respiratory hospitalization, or death during the on-study period as described in Section 5.3.1.1.

Subjects without an event will be censored on the date of last known alive during the double-blind period.

6.7.2.1.4.3. Time (days) from randomization to first adjudicated acute IPF exacerbation

Time (Days) to first acute IPF exacerbation is defined as the number of days from randomization to either the first occurrence of adjudicated acute IPF exacerbation (including both confirmed and suspected cases) as described in Section 5.3.1.1.

Subjects without an event will be censored on the date of last known alive during the double-blind period.

Confidential Page 28 of 56

6.7.2.1.4.4. Time (days) from randomization to all-cause mortality

Subjects without an event will be censored on the last date known alive in the double-blind period. Any survival vital status will be included for early discontinued subjects.

6.7.2.1.4.5. Time (days) from randomization to first adjudicated respiratory hospitalization

Subjects without an event will be censored on the date of last known alive during the double-blind period.

6.7.2.1.4.6. Time (Days) to the first occurrence of composite of adjudicated respiratory hospitalization, absolute FVCpp decline ≥10%, or all-cause death

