APPENDIX 2. ANALYSIS VISIT WINDOWS

Analysis visits are defined by the windows that will have the widths of the corresponding assessments centered at the scheduled time. Unscheduled visits within a visit window defined below will be grouped into the closest scheduled visits based on the visit date.

Table 6: Analysis Visit Window for Vital Signs

Analysis Visit	Target Day	Start Day	End Day	
Baseline		Last value before the first study drug (or randomization date if no infusion		
Day 1 postdose	1	1	1	
Week 3 (predose and postdose)	22	2	32	
Week 6 (predose and postdose)	43	33	53	
Week 9 (predose and postdose)	64	54	74	
Week 12 (predose and postdose)	85	75	95	
Week 15 (predose and postdose)	106	96	116	
Week 18 (predose and postdose)	127	117	137	
Week 21 (predose and postdose)	148	138	158	
Week 24 (predose and postdose)	169	159	179	
Week 27 (predose and postdose)	190	180	200	
Week 30 (predose and postdose)	211	201	221	
Week 33 (predose and postdose)	232	222	242	
Week 36 (predose and postdose)	253	243	263	
Week 39 (predose and postdose)	274	264	284	
Week 42 (predose and postdose)	295	285	305	
Week 45 (predose and postdose)	316	306	326	
Week 48 (predose and postdose)	337	327	351 [\$] or *[@]	
28 Days post last dose [\$]	365	Date of Last dosing+15 [\$]	* [\$]	

^{\$} For subjects who do not enroll OLE only.

Note: The study day with infusions will be used for summary tables whenever possible.

Note: If raw data shows visit is "28 Days post last dose", then set analysis visit=visit

Note: all assessments beyond 60 days post last infusion will be excluded from summary tables or figures.

Confidential Page 41 of 56

^{*} End of the double-blind period (DBP).

[@] For subjects who enroll OLE.

Table 7: Analysis Visit Window for PFT

Analysis Visit	Target Day	Start Day	End Day
Baseline	Last BTR PFT before the first study drug infusion (or randomization date if no infusion received)		
Week 6	43	2	64
Week 12	85	65	106
Week 18	127	107	148
Week 24	169	149	211
Week 36	253	212	295
Week 48	337	296	End of DBP

Table 8: Analysis Visit Window for HRCT

Analysis Visit	Target Day	Start Day	End Day
Baseline	Last value before the first study drug infusion (or randomization date if no infusion received)		
Week 24	169	2	253
Week 48	337	254	End of DBP

Table 9: Analysis Visit Window for Labs

Analysis Visit	Target Day	Start Day	End Day
Baseline	Last value before the first study drug infusion (or randomization date if no infusion received)		
Week 12	85	2	127
Week 24	169	128	211

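### The Cox models relating Week 24 QLF change to survival accept any scan from Day 2 to Day 253 and set no time origin or landmark, so early withdrawal can shift the hazard ratio either way

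*SAP*

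**What the plan says.** OLE SAP Appendix 2 sets out Cox models of overall survival that "will be performed for the ITT population including both double-blind and OLE periods". Two of them use post-baseline change as the predictor, the first of these "to investigate the association between change from baseline in QLF% (baseline to Week 24) and OS". For QLF% the predictor is the "category in change from baseline in QLF% (e.g., ≥2% vs <2%) as the predictor variable"; for QLF volume the example cut is 40 mL. Of missing values it says "No imputation will be performed on missing data". It gives no time origin, landmark, delayed entry or Week 24 window of its own.

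The OLE SAP Introduction refers to the double-blind SAP for rules it does not restate. Section 5.5 of that SAP assigns visits by date rather than by CRF label and takes the last value in a window; HRCT is not among its exceptions. The limits are in "Table 8: Analysis Visit Window for HRCT", whose row reads "Week 24 169 2 253" (target, start and end day). OLE SAP Table 3 has the same day limits for EX-Week 24, but counts them from the first OLE dose, so that is a different window.

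Protocol 4.4 governs the scan at early termination: "HRCT does not have to be repeated, if the last one (excluding the screening visit) was performed within 4 months of this visit". A subject who withdraws before the Week 24 scan is therefore due one. The same section has vital status checked by phone at Weeks 24 and 48. The only mortality definition in either SAP is in double-blind SAP 6.7.2.1.4.4, "Time (days) from randomization to all-cause mortality"; it covers the double-blind period.

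**The concern.** The predictor is meant to be 24 weeks of change, but it can be measured over any interval from one day to 36 weeks and is compared with one fixed cut-off. The short intervals are not a random sample, because most come from subjects who left the study. If those subjects also die at a different rate, time on study before the scan is mixed with prognosis, and the hazard ratio for QLF change picks up both.

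The analysis is meant to show whether worsening QLF goes with mortality, and QLF volume is a ranked secondary endpoint. A hazard ratio pushed down would hide a real association; one pushed up would support QLF as a predictor for the wrong reason. The confidence interval would reflect neither.

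**Working it through.** **1. The window.** Its end is the midpoint of the Week 24 and Week 48 targets: (169 + 337)/2 = 253, which reproduces Table 8. Its start is the first post-baseline day. It reaches 169 - 2 = 167 days before the target and 253 - 169 = 84 days after it. A symmetric window would start at 169 - 84 = Day 85.

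**2. What an early scan carries.** If change accrues in proportion to time, a Day 40 scan holds 39/168 = 23% of the 24-week change, and a Day 85 scan 84/168 = 50%.

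**3. How many subjects.** Protocol 8.1 allows about 20% dropout. Spread evenly over 48 weeks, that is 10% before Week 24, or 34 of 340. Some withdrawers will not be scanned, so 5% (17) is also used. Both shares are assumptions.

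**4. Simulation with no true association.** The documents give no hazard ratio or event count for this analysis, so all inputs are assumed:
- mean QLF% change of 2 points per 24 weeks, between-subject SD 2.5, measurement SD 1, cut at 2 points;
- 10% mortality per 48 weeks, follow-up to Day 700;
- withdrawal uniform over Day 2-162 with a scan that day, other scans on Day 162-176;
- no covariates.

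With no extra change on ET scans, about 25% of early scans reach the cut, against 50% of the others. With 10% early withdrawal, survival counted from randomization and all scans used, the hazard ratio for high versus low change is:

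| Extra QLF% points on ET scans | Threefold mortality | Fivefold mortality |
|---|---|---|
| 0 | 0.84 | 0.76 |
| about 1.5 | near 1 | near 1 |
| 3 | 1.25 | 1.43 |

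If withdrawers have the same mortality as others and ET scans show no excess, it is 0.98. Over 5-10% withdrawal the ranges are 0.76-0.89 with no excess and 1.14-1.43 with 3 extra points. Separate runs agree to about 0.03.

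**5. Simulation with a true association.** Assumed: slope mean 1.5 and SD 2.5 points per 24 weeks, hazard ratio 1.8 per SD of slope, threefold mortality after withdrawal, 5% or 10% early withdrawal. On-time scans alone give 2.32-2.35. Using any scan gives 1.93-2.14 with no excess on ET scans, 2.36-2.55 with 1.5 extra points and 2.60-3.04 with 4 extra points.

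**6. Which element does the harm.** With on-time scans only, counting from randomization gives 2.353 and a Day 176 landmark 2.356, so the origin alone does almost nothing. In the step 4 set-up, delayed entry at the scan date moves the threefold, no-excess case only from 0.84 to 0.88. In step 5, a Day 253 landmark that keeps all scans still gives 2.20-2.28 with no excess and 2.43-2.56 with 4 extra points. The variable scan day is the main source.

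**7. Scale.** With about 40 deaths and 41% of subjects in the high-change group, SE(log HR) is about 1/sqrt(40 x 0.41 x 0.59) = 0.32. The largest downward shift is ln 0.76 = -0.27, or 0.27/0.32 = 0.86 SE. The largest upward shift is ln 1.43 = 0.36, or 0.36/0.32 = 1.1 SE.

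**8. After the change.** Scans on Day 127-211 with a Day 211 landmark bring every step 4 setting to about 0.94-1.07. The share of subjects analysed falls from about 95% to about 86-90%.

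**The case against.** The best counter-argument is that direction and size both rest on assumptions. Protocol 2.6.3 reports IPF progression as the most frequent cause of discontinuation in the open-label phase 2 study. ET scans may then show more change than time alone would give, which offsets or reverses a downward bias. That stands. A reader might infer that early scans must enter as low change and push the hazard ratio below 1; the documents do not support it.

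A reader might also take it as stated that survival runs from randomization, and that guaranteed survival up to the scan is the main fault. OLE SAP Appendix 2 states no origin; randomization is a fair inference from a definition written for the double-blind period only. Step 6 shows that guaranteed survival adds little once scan days are alike.

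The inputs may also be high. The 20% allowance is not said to exclude deaths, which yield no ET scan. Subjects who stop drug are encouraged to stay for all assessments and would then have an on-time scan. The simulation follows everyone to Day 700, whereas planned vital-status calls to withdrawers stop at Week 48; with censoring there, both shifts are smaller.

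Finally, the analysis is outside the alpha-controlled sequence (double-blind SAP 6.7), OLE SAP 5.3.4 disclaims formal inference, and the cut-offs are only examples. This limits the priority. It does not remove the fault, because the date-based window is a stated rule and nothing in OLE SAP Appendix 2 overrides it.

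**Conclusion.** The concern holds in a limited form. OLE SAP Appendix 2 leaves the time origin and landmark unstated and, by cross-reference, treats a scan from any day between Day 2 and Day 253 as a 24-week measurement. When early withdrawers differ in mortality, the hazard ratio partly describes who withdrew early.

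The sign is unknown before the data are seen. It depends on whether ET scans show only time-proportional change or an added rise in fibrosis, and it turns at an excess of roughly 1 to 1.5 points, within the assumed between-subject SD of 2.5. The downward shift stays below one SE of log HR at about 40 deaths; the most extreme upward case slightly exceeds it. More deaths would shrink the SE but not the bias.

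No treatment-effect conclusion depends on these models, and the baseline-QLF models are not affected. This is a cheap improvement to an exploratory analysis.

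**What to change.** In OLE SAP Appendix 2, for the two change-in-QLF models only:
- use HRCTs dated Day 127-211 (169 ± 42 days, Week 24 ± 6 weeks; close to the Day 128-211 window that the double-blind SAP uses for labs and questionnaires);
- include subjects alive and under follow-up at Day 211, and count survival from Day 211;
- add a sensitivity analysis that leaves out all ET scans, since some may still fall between Day 127 and the usual Week 24 visit.

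Leave the baseline-QLF models unchanged and state their time origin as randomization. Both parts of the main change are needed, because a landmark or delayed entry alone leaves much of the bias.

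The cost is a few sentences and a small program change. Early ET scans, late scans on Day 212-253 and deaths before Day 211 leave this analysis. In simulation that is about 5-9 percentage points of subjects. The simulation had no late scans, so the real loss may be somewhat larger: Protocol 6.1.6 moves a missed HRCT to the next scheduled visit.

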5.2. Analysis Sets

5.2.1. Intent-to-Treat Population (ITT)

The intent-to-treat population includes all randomized subjects. Subjects will be analyzed according to their randomized treatment arm regardless of the actual study treatment received.

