6.3. Demographics and Baseline Characteristics

6.3.1. Demographics and Baseline Characteristics

Demographics and important baseline characteristics will be summarized for the ITT by treatment arm and all pooled. These may include but are not limited to age, age group (≤64, 65-74, ≥75), sex, ethnicity, race group, weight, body mass index (BMI), smoking history, prior treatment with an approved IPF therapy (Yes/No), GAP stage (I, II, III), and years since the first diagnosis of IPF. Age is defined as the age on the day of signing the informed consent form (ICF). Years since the first diagnosis will be derived using the formula: date of ICF- date of IPF diagnosis+1. Partial missing date of IPF diagnosis will be imputed as Jan. 01 (if month is missing), or 01 (if day is missing).

Baseline values for efficacy assessments will be presented in baseline tables as appropriate.

Comparability of baseline characteristics between treatment groups will be assessed using analysis of variance (ANOVA) model for continuous variables and Chi-squared test for categorical variables. The nominal p-values will be presented for reference only.

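### The two Week 24 QLF-change survival models in the OLE SAP pool both arms without adjusting for randomized arm

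*SAP*

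**What the plan says.** OLE SAP Appendix 2 states that the Cox analyses "will be performed for the ITT population including both double-blind and OLE periods". The double-blind SAP, section 5.2.1, defines that set: "The intent-to-treat population includes all randomized subjects". Both arms are therefore pooled, over both periods.

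The appendix lists five analyses. Three use baseline QLF as the predictor: QLF% by cutoff, volume by cutoff, and either one as a continuous variable. Two use change from baseline to Week 24:

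- **QLF%:** "the Cox PH model will include EDC GAP stage (I/II/III), prior IPF treatment (Yes/No), and baseline QLF% (as a continuous variable) as covariates", with "category in change from baseline in QLF% (e.g., ≥2% vs <2%) as the predictor variable".
- **QLF volume:** the same model "with baseline QLF% replaced with baseline QLF volume as a continuous covariate", and a change cutoff such as 40 mL.

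The reported contrast is between QLF groups: "The hazard ratio and its corresponding 95% CI between QLF Test Group vs QLF Reference Group". Treatment appears once, in a separate sentence: "A stratified log-rank test stratified by randomization stratification factor will be used for treatment comparison". No within-arm analysis and no arm-by-QLF interaction is planned.

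**The concern.** Baseline QLF is balanced between arms by randomization. Change at Week 24 is not protected in that way, because by then the arms have had 24 weeks of different treatment.

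The sponsor tests for a drug effect on both sides of the association: change in QLF volume and all-cause mortality are both secondary endpoints (double-blind SAP, section 4.2). Protocol section 2.6 reports that QLF change favored pamrevlumab in Phase 2, with a favorable mortality trend. Arm may therefore be a common cause of predictor and outcome.

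Without an arm term, the Week 24 models cannot separate two statements: that subjects whose fibrosis rises die sooner, and that the arm with less rise in fibrosis had fewer deaths. A hazard ratio read as the first could partly be the second.

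**Working it through.** **1. Is arm in the model under another name?** No. Prior IPF treatment is earlier use of an approved therapy (double-blind SAP, section 6.3.1), not study arm. The log-rank test is stratified by the randomization factor, which is GAP stage (section 3.3). The same sentence stands in the double-blind SAP, section 6.7.2.1.5. Whichever groups it compares, it is a separate test and does not adjust the QLF hazard ratio.

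**2. Figures in the plan.** Appendix 2 gives no sample size, event count, power or hazard ratio. The only plan figure used here is the 340 randomized, which is sized on FVC. That figure reproduces: for 120 mL, SD 300 mL, two-sided 0.05 and 90% power, n = 132 per arm, 264 in total, and 264/0.80 = 330, close to 340.

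**3. Hand calculation.** Assumptions, none of them from the documents:

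- 1:1 allocation is the trial's own; a share p0 of placebo and p1 of pamrevlumab subjects fall in the high-change QLF group
- drug hazard ratio for death h
- no effect of QLF on death within either arm
- no crossover

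The arm-weighted mean hazards are (p0 + p1·h)/(p0 + p1) in the high group and ((1−p0) + (1−p1)·h)/(2 − p0 − p1) in the low group. In each case below p0 + p1 = 1, so both denominators are 1.

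| p0 / p1 | h | High / low | Spurious QLF hazard ratio |
|---|---|---|---|
| 60% / 40% | 0.7 | 0.88 / 0.82 | 1.07 |
| 60% / 40% | 0.5 | 0.80 / 0.70 | 1.14 |
| 65% / 35% | 0.5 | 0.825 / 0.675 | 1.22 |

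For context on h: Study 067 had 3 deaths in 50 against 6 in 53 (Protocol section 2.6.3), a crude ratio of 0.060/0.113 = 0.53 from nine deaths. That is too few to treat 0.5 as an expectation.

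**4. Simulation check.** Cox models with QLF category and GAP stage were fitted to 400,000 simulated subjects with two years of follow-up and no QLF effect within arm. Every subject was given a QLF category. The crossover columns let all placebo subjects take on the drug hazard after Week 48.

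| h | p0 / p1 | No arm term, no crossover | No arm term, full crossover |
|---|---|---|---|
| 1.0 | 60% / 40% | 1.002 | 1.003 |
| 0.8 | 60% / 40% | 1.041 | 1.014 |
| 0.7 | 60% / 40% | 1.083 | 1.038 |
| 0.7 | 70% / 30% | 1.151 | 1.074 |
| 0.5 | 60% / 40% | 1.155 | 1.081 |
| 0.5 | 70% / 30% | 1.319 | 1.171 |

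Over the full grid (h from 0.8 to 0.5; 50/40, 60/40 and 70/30) the range was 1.02 to 1.32 without crossover and 1.01 to 1.17 with it. With an arm term the QLF hazard ratio was 0.99 to 1.01 throughout.

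**5. At the trial's size.** These are rejection rates at two-sided 0.05 in 2,000 simulated trials of 340, without crossover, averaging about 59 to 77 deaths. The simulation error near 5% is √(0.05×0.95/2000) ≈ 0.5 percentage points.

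| h | No arm term (60/40; 70/30) | With arm term |
|---|---|---|
| 1.0 | 4.6%; 5.2% | 4.9%; 5.2% |
| 0.7 | 6.5%; 9.8% | 5.7%; 5.3% |
| 0.5 | 8.7%; 19.2% | 4.7%; 4.9% |

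**The case against.** The case for leaving the models alone has several parts, and most of them limit the point.

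- **The association need not be spurious.** A reader might infer that any drug effect on both QLF and survival would show up falsely as QLF predicting death. That goes too far. If the survival effect runs wholly through QLF, the unadjusted association is real. If there is no survival effect, there is no bias. For a purely descriptive prognostic question, conditioning on arm is partly a modelling choice. This stands as a condition on the point. It does not argue against the term, because which case holds is unknown in advance. If QLF carries the effect, the adjusted association should largely remain.
- **The appendix is not only about QLF change.** Three of its five analyses use baseline QLF and are untouched. The stated aim is to investigate association, not to establish a surrogate.
- **Crossover.** It is tempting to count placebo subjects starting pamrevlumab in the extension as a further fault. For this bias it works the other way, and full crossover roughly halves it. Entry is optional, so the truth lies between the two simulated columns.
- **Size.** With 60 to 77 deaths and equal QLF groups, the standard error of the log hazard ratio is about 2/√77 = 0.23 to 2/√60 = 0.26. A spurious ratio of 1.14 (log 0.13) is about half of that. The highest rejection rates need a drug hazard ratio of 0.5 and no crossover.
- **Time at risk.** A reader might also ask for the clock to start at the Week 24 scan, on the ground that subjects must survive to be scanned. The appendix states no time origin, and it rules out imputation, so subjects without a Week 24 scan drop out of these models. Those who remain cannot die before their own scan, and pre-scan time carries essentially no events. Only the spread of scan dates (Days 2 to 253 in the double-blind SAP's HRCT window table) could matter, and the documents give nothing to size it.
- **Status.** The analysis is outside the fixed testing sequence (double-blind SAP, section 6.7, Table 3), and its cutoffs are given only as examples.

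What remains is that a post-randomization predictor is modelled across both arms with no arm term.

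**Conclusion.** The omission is real and confined to the two Week 24 change models. It biases the QLF hazard ratio only if pamrevlumab affects both QLF and survival, with the survival effect at least partly outside QLF. Under the hand-calculated assumptions the spurious ratio is about 1.07 to 1.22. It shrinks with crossover and is 1.00 with no survival effect. The QLF category rates and the drug's mortality effect are assumptions; the documents supply neither. The simulation left out baseline QLF and prior IPF treatment, so it shows direction and order of size, not a forecast.

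This could inflate a modest association, or create part of one. It would not produce a large hazard ratio alone. The documents do not support reading it as a flaw in the whole appendix, as a threat to any primary or secondary conclusion, or as a reason to change the time origin. It is a worthwhile, low-cost improvement to an exploratory analysis.

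**What to change.** In OLE SAP Appendix 2, add randomized arm as a covariate or as a stratum to both Week 24 change models (QLF% and QLF volume). As a covariate this costs one degree of freedom. As a stratum it adds no coefficient, and it lets the hazard in each arm change shape when placebo subjects start pamrevlumab. Hazard ratios within each arm could be shown alongside as description. No new data are needed, and the baseline-QLF models and the time origin can stay as they are.
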